## SAP Amendments before database lock

Version	Issue Date	Section	Revision / Addition	Rationale
2.0	21-Aug-2024	5.11	Added note regarding Glial Fibrillary Acidic Protein (GFAP) and Neurofilament light (NfL) level measurements; however, analysis is still defined separately and will not be part of this SAP.	To clarify the timing of collection and analysis of GFAP and NfL.
3.0	24-Oct-2024	2.3, 5.10.2.1, 5.10.2.2	Analysis approach section updated to remove MMSE baseline score covariate and add baseline value of the endpoint being evaluated as a covariate.	Error in the SAP version 2.0 corrected.
		2.3, 5.10.2.1, 5.10.2.2	Updated strata covariate to use dichotomous strata by combining 'cholinesterase inhibitor therapy alone' and 'memantine therapy [with or without cholinesterase inhibitor therapy]' strata into one.	To clarify use of dichotomous strata for statistical analysis.
		5.1.1	Enrolled Set is renamed as Screened Set.	The name 'Enrolled Set' updated to clearly indicate the subjects to be included.
		5.1.3	Specified the cognitive assessments applicable for the mITT analysis set definition	To clarify the tests to be considered for identifying subjects in mITT analysis set.
		5.2.3	Baseline definition for CDR-SB score is updated to Day 1 assessment instead of average of screening and Day 1 assessment.	To clarify the assessment to be used for baseline.
		5.2.23	Updated to clarify for analysis randomization strata will be dichotomized as: 'cholinesterase inhibitor therapy' vs. 'no cholinesterase use'	To clarify use of dichotomous strata for statistical analysis.

QMD Ref: Worldwide-TMP-ST-054-1.0_Effective: 12Aug2022	Governing QMD: Worldwide-SOP-ST-026
Confidentiality Statement	
This document is the property of Worldwide Clinical Trials Inc. and may not be duplicated, copied, altered or removed from company without prior approval from Worldwide Quality Assurance or in compliance with Worldwide Standard Operating Procedures.	

Worldwide Clinical Trials Controlled Quality Management Document		
 WORLDWIDE CLINICAL TRIALS	Sponsor:	EIP Pharma, Inc.
	Protocol Number:	EIP21-NFD-504
STATISTICAL ANALYSIS PLAN		

	5.10.2.3, 5.10.3.1, 5.10.3.2, 5.10.3.3, 5.10.4.3.1	Subgroup analysis for cholinesterase inhibitor therapy subgroup (Yes/No) is added	To further explore the data based on cholinesterase inhibitor therapy
	5.10.4.3.1	Text added to clarify analysis approach for NIP.	Text inadvertently omitted in previous version of SAP.
	5.12.2	A table for Abnormal liver function test results is added	For additional safety reporting
	10	Text changes and new tables are included	To align with changes to SAP text.

QMD Ref: Worldwide-TMP-ST-054-1.0 Effective: 12Aug2022	Governing QMD: Worldwide-SOP-ST-026
Confidentiality Statement This document is the property of Worldwide Clinical Trials Inc. and may not be duplicated, copied, altered or removed from company without prior approval from Worldwide Quality Assurance or in compliance with Worldwide Standard Operating Procedures.	

Worldwide Clinical Trials Controlled Quality Management Document		
 WORLDWIDE CLINICAL TRIALS	Sponsor:	EIP Pharma, Inc.
	Protocol Number:	EIP21-NFD-504
STATISTICAL ANALYSIS PLAN		

## LIST OF ABBREVIATIONS

Abbreviation	Definition
ADCS-CGIC	Alzheimer's Disease Cooperative Study – Clinical Global Impression of Change
AE	Adverse Event
ATC	Anatomic Therapeutic Chemical
CDR-SB	Clinical Dementia Rating Scale-Sum of Boxes
CI	Confidence Interval
CFT	Category Fluency Test
CS	Clinical Significance
CSR	Clinical Study Report
C-SSRS	Columbia-Suicide Severity Rating Scale
CT	Computed Tomography
DCFS	Dementia Cognitive Fluctuations Scale
DLB	Dementia with Lewy Bodies
DSMB	Data Safety Monitoring Board
ECG	Electrocardiogram
eCRF	Electronic Case Report Form
EEG	Electroencephalography
ET	Early Termination
FAS	Full Analysis Set
IRT	Interactive Response Technology
LFT	Letter Fluency Test
MAR	Missing at Random
MDS-UPDRS	Movement Disorder Society – Unified Parkinson's Disease Rating Scale
MI	Multiple Imputation
mITT	Modified Intent to Treat
MMRM	Mixed Model for Repeated Measures
MMSE	Mini Mental State Examination
MNAR	Missing Not at Random

### Confidentiality Statement

This document is the property of Worldwide Clinical Trials Inc. and may not be duplicated, copied, altered or removed from company without prior approval from Worldwide Quality Assurance or in compliance with Worldwide Standard Operating Procedures.

Worldwide Clinical Trials Controlled Quality Management Document		
 WORLDWIDE CLINICAL TRIALS	Sponsor:	EIP Pharma, Inc.
	Protocol Number:	EIP21-NFD-504
STATISTICAL ANALYSIS PLAN		

Abbreviation	Definition
MRI	Magnetic Resonance Imaging
NCS	Not Clinically Significant
NPI-12	12-item Neuropsychiatric Inventory
NTB	Neuropsychological Test Battery
PSG	Polysomnography
pTau	Phospho-tau
RBD	REM sleep behavioral disorder
SAP	Statistical Analysis Plan
SE	Standard Error
TEAE	Treatment-emergent Adverse Event
TFL	Table, Figure, Listing
TID	Three times daily
TUG	Timed Up and Go Test

## 1 INTRODUCTION

This document details the planned statistical analyses for EIP Pharma, Inc, Protocol ‘EIP21-NFD-504’ study titled “A Phase 2b Clinical Study of the P38 Alpha Kinase Inhibitor Neflamapimod in Patients with Dementia with Lewy Bodies (DLB)”.

The proposed analyses are based on the contents of protocol version 2.0 (dated 15-Dec-2023 (US) / 20-Jun-2023 (Ex-US)).

This is a Phase 2b, multi-center, randomized, double-blind, placebo-controlled 16-week confirmatory (Phase 2b) treatment study of neflamapimod 40 mg vs matching placebo (randomized 1:1) administered with food for 16 weeks in subjects with Dementia with Lewy Bodies (DLB). All subjects will be administered 1 capsule of neflamapimod 40 mg capsules or matching placebo, orally TID with food (i.e., with the morning, mid-day, and evening meals) for 16 weeks. Doses should be administered at least 3 hours apart. The primary objective of this study is to assess the efficacy of neflamapimod, compared to placebo, as a treatment for DLB, as assessed by the Clinical Dementia Rating Scale-Sum of Boxes (CDR-SB).

## 2 STUDY OBJECTIVES, ENDPOINTS, AND ESTIMANDS

### 2.1 Objectives

#### 2.1.1 Primary Objective

The primary objective is to compare the efficacy of neflamapimod with placebo, as a treatment for DLB, as assessed by the CDR-SB.

#### 2.1.2 Secondary Objectives

The secondary objectives are to:

- Demonstrate that neflamapimod improves motor function, compared to placebo, as assessed by the Timed Up and Go Test (TUG).
- Demonstrate that neflamapimod improves cognition, compared to placebo, as assessed by a DLB-specific Neuropsychological Test Battery (NTB). The NTB is comprised of:
  - Cogstate Detection test (DET)
  - Cogstate Identification test (IDN)
  - Cogstate One Card Learning test (OCL)
  - Cogstate One Back test (ONB)
- Demonstrate that neflamapimod improves global (cognition, function and behavior) disease status as evaluated by a clinician with caregiver input, compared to placebo, as

QMD Ref: Worldwide-TMP-ST-054-1.0 Effective: 12Aug2022	Governing QMD: Worldwide-SOP-ST-026
Confidentiality Statement	
This document is the property of Worldwide Clinical Trials Inc. and may not be duplicated, copied, altered or removed from company without prior approval from Worldwide Quality Assurance or in compliance with Worldwide Standard Operating Procedures.	

Worldwide Clinical Trials Controlled Quality Management Document		
 WORLDWIDE CLINICAL TRIALS	Sponsor:	EIP Pharma, Inc.
	Protocol Number:	EIP21-NFD-504
STATISTICAL ANALYSIS PLAN		

assessed by the Alzheimer's Disease Cooperative Study – Clinical Global Impression of Change (ADCS-CGIC).

### 2.1.3 Exploratory Objectives

- Evaluate the effect of neflamapimod on attention, as assessed by Cogstate Detection and Identification tests
- Evaluate effect of neflamapimod on cognitive fluctuations, as assessed by the Dementia Cognitive Fluctuations Scale (DCFS).
- Evaluate the effect of neflamapimod on select domains of the 12-item Neuropsychiatric Inventory (NPI-12), including depression (dysphoria), apathy, hallucinations, and agitation/aggression.
- Evaluate the effect of neflamapimod on visual hallucinations, as assessed by hallucinations frequency x severity score within the NPI-12 in subjects who report hallucinations at baseline.
- Evaluate the effect of neflamapimod on sleep and night-time behavior scores within the NPI-12.
- Evaluate the effect of neflamapimod on MDS-UPDRS3 motor examination (Part III) score.
- Evaluate the effect of neflamapimod on quantitative EEG parameters associated with cholinergic function, specifically, change in beta functional connectivity and in alpha reactivity.
- Evaluate the effect of neflamapimod on basal forebrain atrophy, as assessed by Nucleus of basalis of Meynert (NbM) volumetry by structural MRI.

## 2.2 Endpoints

### 2.2.1 Primary Endpoint

- Change from Baseline in CDR-SB during the double-blind treatment phase

### 2.2.2 Secondary Endpoints

- Change from Baseline in TUG during the double-blind treatment phase
- Change from Baseline in the composite score of the NTB, including tests of attention and visual learning, during the double-blind treatment phase
- ADCS-CGIC score at Week 16 at the end of the double-blind treatment phase

QMD Ref: Worldwide-TMP-ST-054-1.0_Effective: 12Aug2022	Governing QMD: Worldwide-SOP-ST-026
Confidentiality Statement This document is the property of Worldwide Clinical Trials Inc. and may not be duplicated, copied, altered or removed from company without prior approval from Worldwide Quality Assurance or in compliance with Worldwide Standard Operating Procedures.	

Worldwide Clinical Trials Controlled Quality Management Document		
 WORLDWIDE CLINICAL TRIALS	Sponsor:	EIP Pharma, Inc.
	Protocol Number:	EIP21-NFD-504
STATISTICAL ANALYSIS PLAN		

### 2.2.3 Exploratory Endpoints

- Change from Baseline in Attention composite score, including two tests within the NTB that evaluates attention (Detection and Identification)
- Change from Baseline in Dementia Cognitive Fluctuations Scale (DCFS)
- Change from Baseline to the end of the double-blind treatment period (average of Week 12 and Week 16) in select domains of the 12-item Neuropsychiatric Inventory (NPI-12), including depression (dysphoria), apathy, hallucinations, and agitation/aggression.
- For subjects who report hallucinations at Baseline, change from baseline to the end of the double-blind treatment period (average of Week 12 and Week 16) in hallucinations frequency x severity score within the NPI-12.
- Change from Baseline to the end of the double-blind treatment period (average of Week 12 and Week 16) in sleep and night-time behavior change within the NPI-12.
- Change from Baseline during the double-blind treatment period in MDS-UPDRS3 motor examination (Part III) score.
- Change from Baseline to Week 16 in beta functional connectivity and in alpha reactivity on quantitative EEG.
- Basal forebrain atrophy by structural MRI (Ex-US only)

## 2.3 Estimand

The following estimand attributes are defined with regards to the primary efficacy endpoint analysis:

**Objective:** The primary objective is to compare the efficacy of neflamapimod with placebo, as a treatment for DLB, as assessed by the CDR-SB

**Estimand:** What is the effect of neflamapimod in the treatment of DLB, as assessed by the CDR-SB.

**Treatment:** Neflamapimod 40mg vs placebo

ESTIMAND	ANALYSIS
Target population	Analysis set
Patients with DLB as defined by the study eligibility criteria	Modified Intent-To-Treat (mITT) Analysis Set, which consists of subjects who are randomized receive at least one dose of study drug and at least one post-dose cognitive assessment.
Variable	Outcome measure
CDR-SB Score	Change from baseline in the CDR-SB Score
Handling of intercurrent events	Handling of missing data

#### Confidentiality Statement

This document is the property of Worldwide Clinical Trials Inc. and may not be duplicated, copied, altered or removed from company without prior approval from Worldwide Quality Assurance or in compliance with Worldwide Standard Operating Procedures.

Worldwide Clinical Trials Controlled Quality Management Document		
 WORLDWIDE CLINICAL TRIALS	Sponsor:	EIP Pharma, Inc.
	Protocol Number:	EIP21-NFD-504
STATISTICAL ANALYSIS PLAN		

 
• Use of prohibited concomitant medication
 
• Non-compliance to protocol (e.g., poor treatment adherence, use of prohibited medication and other protocol deviations)
 
 
All these intercurrent events (ICEs) are assumed to be well-balanced events across both randomized arms and should not affect the estimation of the treatment effects. Therefore, all observed data will be used regardless of the occurrence of these intercurrent events (Treatment-policy strategy).
	
Primary Analysis: Only observed data will be used in the linear effects model. Missing data will NOT be imputed.
 
Sensitivity Analysis: All missing data will be handled by Multiple Imputation (MI) under an assumption of missing not at random (MNAR) using pattern mixture model such as control-based imputation (i.e., placebo arm reference).

Population-level summary measure
 
The difference between treatment arms in the average change from Baseline of the CDR-SB during the double-blind treatment phase.
	
Analysis approach
 
The difference between treatment arms in the average change from Baseline of the CDR-SB score will be estimated from a linear mixed effects model, including treatment group, time in weeks, and treatment by time interaction as fixed effects; stratification factors (with and without cholinesterase inhibitor therapy), sex and baseline value as covariates. The random effect is on the subject term.
 
A sensitivity analysis will be performed based on MNAR imputed data, the model will be fit across all imputed datasets and results will be pooled using Rubin's rules to obtain a single treatment effect estimate.

### 3 SAMPLE SIZE

The primary hypothesis for the study is that neflamapimod will significantly improve outcome vs. placebo on the CDR-SB. To demonstrate this effect, a total of approximately 160 subjects are planned to be enrolled, of whom 80 are planned to receive neflamapimod and 80 are planned to receive placebo. Sample size was determined by power analysis via simulations, conducted by utilizing outcomes in the CDR-SB in neflamapimod 40mg TID and placebo groups in the Phase 2a clinical study in DLB (Study 501), to generate for each patient a change from baseline in the CDR-SB score at individual visits over the course of the simulated clinical study, and then analyzing the result of each clinical study utilizing the linear mixed effects model for repeated measures that will

QMD Ref: Worldwide-TMP-ST-054-1.0\_Effective: 12Aug2022

Governing QMD: Worldwide-SOP-ST-026

## 4 RANDOMIZATION

Subjects will be stratified by background dementia therapy (one of three strata: no cholinesterase inhibitor therapy, cholinesterase inhibitor therapy alone, or memantine therapy [with or without cholinesterase inhibitor therapy]), and then randomized on a 1:1 basis in a blinded manner to receive either placebo or 40 mg neflumapimod utilizing an automatically generated random code. Randomization will be administered via Interactive Response Technology (IRT).

## 5 PLANNED ANALYSES

The Statistical Analysis Plan (SAP) and Table, Figure, Listing (TFL) Shells (and any amendments) must be approved prior to breaking of the blind for the primary and secondary analysis. If post database lock, additional statistical analyses or changes to the statistical analysis are required, then those will be documented in a Post Database Lock Statistical Analysis Plan Addendum.

### 5.1 Analysis Sets

#### 5.1.1 Screened Set

The Screened Set includes all subjects who gave informed consent.

#### 5.1.2 Full Analysis Set

The Full Analysis (FAS) Set includes all subjects who were randomized into any treatment group. Subjects will be analyzed according to the study treatment arm to which they were randomly allocated. The FAS will be used for analysis of accountability and demographics.

QMD Ref: Worldwide-TMP-ST-054-1.0 Effective: 12Aug2022	Governing QMD: Worldwide-SOP-ST-026
Confidentiality Statement	
This document is the property of Worldwide Clinical Trials Inc. and may not be duplicated, copied, altered or removed from company without prior approval from Worldwide Quality Assurance or in compliance with Worldwide Standard Operating Procedures.	

Worldwide Clinical Trials Controlled Quality Management Document		
 WORLDWIDE CLINICAL TRIALS	Sponsor:	EIP Pharma, Inc.
	Protocol Number:	EIP21-NFD-504
STATISTICAL ANALYSIS PLAN		

### 5.1.3 Modified Intent-To-Treat Analysis Sets

The Modified Intent-To-Treat (mITT) Analysis Set for the double-blind treatment phase includes all subjects who are randomized and received at least one dose of study drug and who have at least one post-dose cognitive assessment (CDR-SB and/or NTB).

The mITT Analysis Set for the open-label extension phase will include all subjects included in the mITT Analysis Set for the double-blind treatment phase who completed the double-blind treatment phase and continued into the open-label extension phase.

Subjects will be analyzed according to the study treatment arm to which they were randomized. The mITT Analysis Set will be used for efficacy analysis. For outputs corresponding to each treatment phase, the analysis set defined for that corresponding phase will be used.

### 5.1.4 Safety Analysis Sets

The Safety Analysis Set for the double-blind treatment phase will include all subjects who receive at least one dose of study drug.

The Safety Analysis Set for the open-label extension phase will include all subjects who received at least one dose of study drug, completed the double-blind treatment phase, and continued into the open-label extension phase. These subjects will be analyzed according to the actual study treatment received. The Safety Analysis Set will be used for analysis of safety endpoints. For outputs corresponding to each treatment phase, the analysis set defined for that corresponding phase will be used.

### 5.1.5 Completer Analysis Set

The Completer Analysis Set for double-blind treatment phase will include all subjects in Safety Analysis Set who have Week 16 CDR-SB score.

The Completer Analysis Set for the open-label extension phase will include all subjects in double-blind treatment phase completer analysis set, who completed the double-blind treatment phase, and continued into the open-label extension phase. These subjects will be analyzed according to the actual study treatment received. The Completer Analysis Set will be used for summarizing treatment exposure and compliance.

### 5.1.6 Pharmacokinetic (PK) Analysis Set

The PK Analysis Set will include all subjects who received at least one dose of study drug, for whom PK samples were obtained, and for whom sufficient plasma concentrations are available.

## 5.2 Derived Data

QMD Ref: Worldwide-TMP-ST-054-1.0_Effective: 12Aug2022	Governing QMD: Worldwide-SOP-ST-026
Confidentiality Statement  This document is the property of Worldwide Clinical Trials Inc. and may not be duplicated, copied, altered or removed from company without prior approval from Worldwide Quality Assurance or in compliance with Worldwide Standard Operating Procedures.	

Worldwide Clinical Trials Controlled Quality Management Document		
 WORLDWIDE CLINICAL TRIALS	Sponsor:	EIP Pharma, Inc.
	Protocol Number:	EIP21-NFD-504
STATISTICAL ANALYSIS PLAN		

This section describes the derivations required for statistical analysis. Unless otherwise stated, variables derived in the source data will not be re-calculated.

### 5.2.1 Age

Age (years) at informed consent will be reported as calculated in the electronic data case report form.

### 5.2.2 Race

Where more than one race category has been selected for a subject, these race categories will be combined into a single category labelled “Multiple Race” in the summary tables. The listings will reflect the original selected categories.

### 5.2.3 Baseline

For all study endpoints other than the TUG, baseline is defined as the last non-missing value (either scheduled, unscheduled or repeat) before the subject receives the first dose of study drug. Specifically, and for example, for the CDR-SB, the Day 1 value will be utilized for the Baseline value. If the Day 1 value is missing, screening (or repeat screening, if performed) value will be utilized. For the TUG, the mean of screening and Day 1 value will be taken as the Baseline value for analysis purposes.

For re-screened subjects, if assessments are not completed at re-screening, the results from original screening should be used.

If an assessment is scheduled to be made prior to dosing on First study day (SD1) and either time of assessment or time of first dose is missing, then such assessment is considered as prior to the first dose. The exceptions for this rule are AEs, which will be considered as treatment-emergent.

Change from baseline = Result at Visit – Result at baseline.

### 5.2.4 Early Withdrawal Assessments

For the analysis, assessments performed at early withdrawal visits will be mapped to the nearest missed visit, using midpoints between visits to window the early withdrawal. If the early withdrawal assessment is mapped to a visit where a scheduled assessment is already present, the scheduled assessment will take precedence, and the early withdrawal assessment will be disregarded (and listed only).

*Table 1: Early withdrawal mapping for scheduled visits of Double-Blind Treatment Phase*

Assessment(s)	Timing of Early Withdrawal Assessment	Mapped Visit
---------------	---------------------------------------	--------------

QMD Ref: Worldwide-TMP-ST-054-1.0_Effective: 12Aug2022	Governing QMD: Worldwide-SOP-ST-026	
Confidentiality Statement		

This document is the property of Worldwide Clinical Trials Inc. and may not be duplicated, copied, altered or removed from company without prior approval from Worldwide Quality Assurance or in compliance with Worldwide Standard Operating Procedures.

Worldwide Clinical Trials Controlled Quality Management Document		
 WORLDWIDE CLINICAL TRIALS	Sponsor:	EIP Pharma, Inc.
	Protocol Number:	EIP21-NFD-504
STATISTICAL ANALYSIS PLAN		

Physical Examination	Day 2 to Day 117	Week 16
	Day 118 to (Last dose+14 days)	Follow-Up
Vital Signs	Day 2 to Day 17	Week 2
	Day 18 to Day 33	Week 4
	Day 34 to Day 61	Week 8
	Day 62 to Day 89	Week 12
	Day 90 to Day 117	Week 16
	Day 118 to (Last dose+14 days)	Follow-Up
Hematology, Chemistry, C-SSRS, NTB, DCFS	Day 2 to Day 33	Week 4
	Day 34 to Day 61	Week 8
	Day 62 to Day 89	Week 12
	Day 90 to Day 117	Week 16
Coagulation, EEG	Day 2 to Day 117	Week 16
CDR-SB, TUG	Day 2 to Day 61	Week 8
	Day 62 to Day 89	Week 12
	Day 90 to Day 117	Week 16
NPI-12	Day 2 to Day 89	Week 12
	Day 90 to Day 117	Week 16
ADCS-CGIC	Day 2 to Day 117	Week 16
MDS-UPDRS	Day 2 to Day 61	Week 12
	Day 62 to Day 117	Week 16

Table 2: Early withdrawal mapping for scheduled visits of Open-Label Extension Phase

Assessment(s)	Timing of Early Withdrawal Assessment	Mapped Visit
Physical Examination	Day 2 to Day 229	Week 32
	Day 230 to (Last dose+14 days)	Follow-Up
Vital Signs	Day 2 to Day 33	Week 4
	Day 34 to Day 61	Week 8
	Day 62 to Day 117	Week 16
	Day 118 to Day 229	Week 32
	Day 230 to (Last dose+14 days)	Follow-Up
Hematology, Chemistry	Day 2 to Day 33	Week 4
	Day 34 to Day 61	Week 8
	Day 62 to Day 117	Week 16
	Day 118 to Day 229	Week 32
Coagulation	Day 2 to Day 229	Week 32
C-SSRS, CDR-SB, NTB, TUG, ADCS-CGIC, DCFS, NPI-12, MDS-UPDRS	Day 2 to Day 61	Week 8
	Day 62 to Day 117	Week 16
	Day 118 to Day 229	Week 32

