## 5.2.5 Duration / Study Day / Time

First study day (SD1) is defined as the date of first administration of study drug. Study day will be calculated as the number of days from first administration of study drug.

- date of event – SD1 + 1, for events on or after first administration of study drug
- date of event – SD1, for events before first dose.

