### Confidentiality Statement

This document is the property of Worldwide Clinical Trials Inc. and may not be duplicated, copied, altered or removed from company without prior approval from Worldwide Quality Assurance or in compliance with Worldwide Standard Operating Procedures.

Worldwide Clinical Trials Controlled Quality Management Document		
 WORLDWIDE CLINICAL TRIALS	Sponsor:	EIP Pharma, Inc.
	Protocol Number:	EIP21-NFD-504
STATISTICAL ANALYSIS PLAN		

Category 6	Preparatory Acts or Behaviour
Category 7	Aborted Attempt
Category 8	Interrupted Attempt
Category 9	Actual Attempt (non-fatal)
Category 10	Suicide

Suicidal Ideation since baseline – A “yes” answer at any time during double-blind treatment phase to any one of the 5 suicidal ideation questions (categories 1-5) on the C-SSRS.

Suicidal Behaviour since baseline – A “yes” answer at any time during double-blind treatment phase to any one of the 5 suicidal behaviour questions (categories 6-10) on the C-SSRS.

There will be no imputation of missing data for C-SSRS.

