### 5.2.22 Unscheduled Visits

Visit data will be presented using nominal times as collected in the eCRF. Both scheduled and unscheduled post-baseline visits will be tabulated. Unscheduled visits will be presented as ‘Visit x.xx’ (e.g., Visit 3.01).

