### 5.12.2 Laboratory Data

Descriptive statistics of the observed values and change from baseline (continuous data) will be presented by treatment group and visit for each hematology, chemistry, and coagulation parameter. Each measurement (continuous data) will be classed as below, within, or above normal range, based on ranges supplied by the laboratory used. Shift tables in relation to the normal range from baseline to each follow-up visit will be presented.

Further, number (%) of patients that meet the following cut-off points at baseline and each post-baseline visit will be presented:

- ALT >3 x ULN

QMD Ref: Worldwide-TMP-ST-054-1.0_Effective: 12Aug2022	Governing QMD: Worldwide-SOP-ST-026
Confidentiality Statement This document is the property of Worldwide Clinical Trials Inc. and may not be duplicated, copied, altered or removed from company without prior approval from Worldwide Quality Assurance or in compliance with Worldwide Standard Operating Procedures.	

Worldwide Clinical Trials Controlled Quality Management Document		
 WORLDWIDE CLINICAL TRIALS	Sponsor:	EIP Pharma, Inc.
	Protocol Number:	EIP21-NFD-504
STATISTICAL ANALYSIS PLAN		

- ALT >5 x ULN
- ALT >8 x ULN
- AST >3 x ULN
- AST >5 x ULN
- AST >8 x ULN
- ALT or AST >3 x ULN
- ALT or AST >5 x ULN
- ALT or AST >8 x ULN
- Total Bilirubin >1.5 x ULN
- Total Bilirubin >2 x ULN
- (ALT or AST >3 x ULN) and (Total Bilirubin > 2 x ULN or INR >1.5)\*

\*For multi-parameter categories, parameter values must be from the same sample (e.g., have same sample date).

All laboratory data will be listed.

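### The early-withdrawal precedence rule in SAP 5.2.4 also covers safety data, so a withdrawal-visit laboratory, vital-sign or C-SSRS result can drop out of the by-visit safety tables and be listed only

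*SAP*

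**What the plan says.** SAP 5.2.4 says that a withdrawal assessment is "mapped to the nearest missed visit, using midpoints between visits to window the early withdrawal". If the visit it lands on already holds a scheduled result, "the scheduled assessment will take precedence, and the early withdrawal assessment will be disregarded (and listed only".

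The rule has no exception for safety data, and the mapping tables include it:

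- Table 1 (double-blind) has one set of windows for "Hematology, Chemistry, C-SSRS, NTB, DCFS" and another for vital signs.
- Table 2 (extension) has windows for vital signs, hematology and chemistry, and groups C-SSRS with the efficacy scales: "C-SSRS, CDR-SB, NTB, TUG, ADCS-CGIC, DCFS, NPI-12, MDS-UPDRS".

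The safety outputs that use these data are by visit. For the liver cut-offs, 5.12.2 says "number (%) of patients that meet the following cut-off points at baseline and each post-baseline visit will be presented". Laboratory shifts run from baseline to each visit (5.12.2), vital signs are shown by group and visit (5.12.3), and the C-SSRS shift is by treatment and visit (5.12.6). None of these sections specifies a summary over all post-baseline results.

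Two other sections bear on the point. 5.2.22 says "Both scheduled and unscheduled post-baseline visits will be tabulated". 5.2.21 defines suicidal ideation since baseline as a yes answer "at any time during double-blind treatment phase to any one of the 5 suicidal ideation questions", and defines suicidal behaviour in the same way.

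**The concern.** A repeated-measures efficacy model needs one value per subject per visit, so a precedence rule makes sense there. Descriptive safety tables do not need it, and 5.2.22 shows that the SAP accepts extra results in them.

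Take a hypothetical subject whose Week 8 visit on Day 57 shows ALT 2.5 x ULN and a negative C-SSRS. The subject withdraws on Day 60 with ALT 6 x ULN or a yes to an ideation item. Table 1 sends Day 60 to Week 8, the Day 57 values stand, and the Day 60 values are listed only. The counts above 3 x and 5 x ULN and the C-SSRS shift table do not show this subject as positive. Had the same sample been labelled unscheduled, 5.2.22 would have put it in the tables.

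At stake is the completeness of safety counts in subjects who stop early. Rows such as ALT above 5 x or 8 x ULN, or suicidal ideation, are likely to hold few subjects, so one omitted result could be visible.

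**Working it through.** The SAP gives no figure for this, so there is none to reproduce. The check counts the days on which a withdrawal assessment would meet a scheduled result already in its window.

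**Inputs**
- Table 1 windows for hematology, chemistry and C-SSRS: Days 2-33, 34-61, 62-89 and 90-117, for Weeks 4, 8, 12 and 16.
- Table 1 windows for vital signs: the same, except that Days 2-17 go to Week 2 and Days 18-33 to Week 4.
- Study day (5.2.5): "date of event – SD1 + 1, for events on or after first administration of study drug". First dose is Day 1, so Week w is taken as Day 7w + 1: Days 15, 29, 57, 85 and 113 (assumption: visits on time).
- Planned dropouts (section 3): 10% of 160 = 16.

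**Formula.** Collision days per window = window end - scheduled visit day. Share = sum / 116, since Days 2 to 117 are 116 days.

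**Hematology, chemistry and C-SSRS, double-blind**
- Week 4: 33 - 29 = 4 (Days 30-33)
- Week 8: 61 - 57 = 4 (Days 58-61)
- Week 12: 89 - 85 = 4 (Days 86-89)
- Week 16: 117 - 113 = 4 (Days 114-117)

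The first three give 12/116 = 10.3%. With the days after Week 16, 16/116 = 13.8%. The lower figure is the fairer one, because a subject seen at Week 16 has reached the end of the 16-week treatment phase.

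**Vital signs, double-blind.** Week 2 adds 17 - 15 = 2 days: 14/116 = 12.1%, or 18/116 = 15.5% with the days after Week 16.

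**Extension (Table 2, same convention).** Laboratory tests and vital signs: 16 of 228 days (7%). C-SSRS: 12 of 228 (5%). Both include the 4 days after Week 32.

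**Subjects.** If withdrawal dates are spread evenly over Days 2-117, 16 x 12/116 = 1.7 and 16 x 16/116 = 2.2, so about 2 across both arms. These are collisions. A liver count or C-SSRS cell changes only if the displaced result falls in a different category from the scheduled one, and the SAP gives no rate for that.

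**Sensitivity of the double-blind laboratory and C-SSRS share**

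| Assumption | Without days after Week 16 | With them |
|---|---|---|
| On time, Day 7w + 1 | 12/116 = 10% | 16/116 = 14% |
| On time, Day 7w | 15/116 = 13% | 20/116 = 17% |
| Each visit 3 days early | 21/116 = 18% | 28/116 = 24% |
| Each visit 3 days late | 3/116 = 3% | 4/116 = 3% |
| True midpoints instead of printed ends | 42/116 = 36% | 46/116 = 40% |

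The last row arises because the printed ends (Days 33, 61, 89) are not midpoints. Those would be (29 + 57)/2 = 43, (57 + 85)/2 = 71 and (85 + 113)/2 = 99, giving 14 collision days in each of the first three windows. If the nearest-missed-visit wording were programmed instead, an attended visit would never be a target. No collision would then arise while a scheduled visit remained to be missed.

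**The case against.** The strongest reply is that the mapping sentence points to a missed visit. In the example Week 8 was attended, so the Day 60 result would move to a later visit and be tabulated. That has force on frequency: a reader might infer that the loss is the same wherever the cut-offs lie, and it is not. It does not remove the point. The next sentence of 5.2.4 provides for landing on an occupied visit, and Tables 1 and 2 assign visits by day range alone.

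Three further replies stand in part.

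- **The result is not lost.** All laboratory and C-SSRS data are listed, and a vital-signs listing is planned. An event reported as an adverse event enters the TEAE tables and, where it applies, the table of TEAEs leading to withdrawal. Table 14.3.4.1 (abnormal laboratory values) might show a displaced value, but its content is not defined. A reader might infer that such findings disappear from the report. What is lost is their place in the by-visit tables, from which arms are compared.
- **There is no outright contradiction.** 5.2.21 defines an any-time variable that a by-visit rule need not restrict, and no table title in section 10 reports it. 5.2.22 concerns a different class of visit. The rule sits poorly with both sections, but it contradicts neither.
- **The direction of any bias is not documented.** One might suppose that a withdrawal soon after a visit follows a bad result, so that the dropped value tends to be the worst. The SAP gives no support for this, and the rule equally drops values that have returned to normal.

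The count may also be smaller. The extension approach lists 149 participants. If 160 were randomised (the planned figure; the actual number is not given), 11 did not enter, and 11 x 12/116 = 1.1 to 11 x 16/116 = 1.5 collisions.

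**Conclusion.** The point holds. As written, 5.2.4 removes collected vital-sign, laboratory and C-SSRS results from by-visit safety tables whenever a withdrawal assessment maps to an occupied visit, and no other specified summary of those data restores them.

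The reach is modest: 10% to 14% of double-blind days for laboratory data and C-SSRS, or about 2 of 16 planned dropouts, with only some of these altering a cell. This assumes on-time visits on Day 7w + 1, the printed windows, and withdrawal dates unrelated to visit dates. The mapping wording that is actually programmed could move the share well up or down.

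The primary endpoint and the hierarchical testing are untouched. The change is worth making because it is cheap and the affected rows are likely to be sparse.

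**What to change.** Limit the precedence sentence in 5.2.4 to efficacy by-visit analyses. For vital signs, laboratory data and C-SSRS:

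- tabulate a displaced withdrawal result in its own ET row, footnoted as holding only results whose mapped visit already had a scheduled value;
- include that row in the liver cut-off tables (14.3.7.7a/b) and in the laboratory and C-SSRS shift tables;
- state in 5.2.21 that the any-time ideation and behaviour variables include withdrawal-visit answers.

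A separate worst-post-baseline count is not needed for this repair; the SAP does not specify one. Saying which mapping rule governs (missed visit, midpoint or printed window) would settle how often the ET row is used, but the fix works under any of them.

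The cost is extra rows in the safety shells and some reprogramming; the data are already collected. Because the database is locked and the study unblinded, section 5 of the SAP requires the change to go into a post-lock addendum, where it should be identified as made after unblinding. It adds results to descriptive tables and affects no hypothesis test.
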